Our pilot study which showed a significantly increased change in FRC at the end of the two week treatment period and at discharge in the infants randomized to the additional two weeks of CPAP versus CPAP discontinuation is very encouraging ¹⁶. However the measurements in the pilot study were limited to those done in the NICU and did not measure lung diffusion which currently cannot be measured in the NICU. This new randomized trial will allow us to measure the persistence of the effect of eCPAP on lung volumes and to measure the effect on lung diffusion at six months of age. It will also allow us to measure the effect of eCPAP on forced expiratory flows and other exploratory outcomes including clinical respiratory and neurodevelopmental outcomes.

4. Study Design

[figure not shown]
a. Overview

This is a randomized single-blind Phase 2 trial of eCPAP in 100 stable preterm infants born at 24 to \leq 32 weeks of gestational age (**Figure 9**, Study Overview). Once infants are consented and, meet CPAP stability criteria they will be randomized to one of two groups:

- 1. 2 additional weeks of CPAP (eCPAP)
- 2. CPAP discontinuation as per usual NICU care (dCPAP)

Prior to randomization and at the end of the 2 weeks of treatment, a pulmonary function test (PFT) will be performed. Infants will return to OHSU at approximately 6 months of corrected gestational age (CGA) for pulmonary function (primary outcome of alveolar volume). Neurodevelopmental testing will be done at 6-12 months of age. Infants will be followed up to 1 year of age with monthly respiratory questionnaires that will be completed via phone. The study will be performed at OHSU and at PeaceHealth SouthWest Washington Medical Center (PHSW) and build on [name] strong pilot data¹⁶. It is not feasible or ethical to blind the caregivers and researchers to the randomized intervention in the NICU; however, the 6 month PFTs will be directed by personnel blinded to treatment allocation in the NICU and blinded personnel will administer the monthly respiratory questionnaires and neurodevelopmental assessments. The individual PFTs will be reviewed for acceptability, reproducibility, and completeness by [name], (Co-PI of study) and [name], RRT, an experienced infant pulmonary function technologist. They will be blinded to the treatment allocation as will the statisticians analyzing the final data.

Figure 9. Study Overview

5. Study Population

a. Number of Subjects

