- We anticipate screening 300 infants to recruit the cohort
- Up to 130 infants will be consented once inclusion/exclusion criteria have been verified
- 100 infants will be randomized

b. Inclusion Criteria

- 1) Infants born at >24 to ≤ 32 weeks gestation
- 2) Treated with CPAP for ≥ 24 hours for respiratory distress (either as initial therapy or following extubation)

c. Exclusion Criteria

- 1) Significant congenital heart disease
- 2) Major malformations
- 3) Chromosomal anomalies
- 4) Culture proven sepsis at consent

- 5) Complex maternal medical conditions
- 6) Clinical instability
- 7) Multiple gestations > twins
- 8) <3rd or >97th percentile for weight⁸⁵
- 9) Participating in another neonatal randomized clinical trial with a competing outcome
- **10)** Mother/legal guardian without stable method of communication

Additional criteria that must be met prior to randomization:

- 1) CPAP stability criteria met for at least 12 hours
 - The following CPAP stability criteria 16;86 has to be met for more than 12 hours by 34 weeks of CGA:
 - o CPAP of 5 cmH2O
 - o On room air
 - o Respiratory rate ≤70 bpm without significant retractions
 - <3 self-resolving apneas or bradycardias or desaturations in 1 hour in last 6 hours

 - Average SpO2 >86% for 90% of the last 24 hours
 - Not being treated for a patent ductous or sepsis
 - o Tolerating CPAP "cares"

d. Vulnerable Populations

Neonates will be included in this research. The inclusion of neonates is critical to the research because we have pilot data in preterm infants demonstrating that eCPAP may stimulate lung growth. However, our initial trial did not include follow-up testing after discharge to determine the potential duration of the effect of eCPAP on lung volumes and did not include measurements of lung diffusing capacity. Parent or guardian permission will be obtained before the child will be enrolled in the study, as per IRB guidelines.

e. Setting

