We will do extensive in-servicing with all caregivers working in the both NICUs prior to starting the study outlining the study's rationale. We will present data from our initial study¹⁶ which demonstrated that the infant's participation in the study did not affect length of stay or the time taken to achieve full nipple feeds. We will also discuss the fact that participation in the study will not increase hospitalization costs for the infant (level of hospital charges are based on need for gavage feeds regardless of whether infant is on or off CPAP). These same discussions will be done with the parents, starting far in advance of the infant being consented and meeting randomization criteria. We will also assemble a patient advisory group of a projected four parents who will meet at least twice per year to give advice and feedback on the study elements. These parents will be recruited from the current OHSU NICU family advisory council that meets monthly.

g. Consent Process

Written informed consent will be obtained from each subject's parent/legal guardian prior to any study procedures taking place. Once an eligible infant is identified, individuals authorized to obtain written informed consent (PI, co-investigators, and study staff specifically designated by the PI) will begin the informed consent discussion with the subject's parent(s)/legal guardian. The informed consent process will take place in the NICU or in a quiet, private area.

The information provided in the consent will cover the elements in the CFR Part 50.25 and be approved by the site Institutional Review Board (IRB). This includes the investigational nature and objective of the trial; the procedures and treatments involved and their attendant risks, discomforts, and benefits; and the potential alternative therapies, alternative to not participate and right to withdraw without penalty, all of which will be explained to the parent/legal guardian in detail. All of the parent/legal guardian's questions will be answered before signing the consent form. If the parent/legal guardian wishes to take the consent form home to consult with other family members or health care providers, or to allow more time for consideration, they will be allowed to do so. A copy of the signed consent form will be given to the parent/legal guardian.

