Infant pulmonary function testing will be performed when CPAP stability criteria is met prior to randomization and at the end of the two week treatment period. Studies will be performed with the infant supine, quietly asleep and at least 30 minutes after a feed. All measurements will be obtained using a computerized infant pulmonary function cart (SensorMedics 2600; SensorMedics Inc, Yorba Linda, CA; Jaeger/Viasys Master Screen Baby Body) in the OHSU NICU at the infant's bedside. Standard testing criteria outlined by the American Thoracic Society / European Respiratory Society will be met ^{81;93,94}. Tidal breathing will be recorded with up to 50 flow-volume loops⁴⁶. Passive respiratory mechanics (respiratory compliance [Crs] and respiratory resistance [Rrs]) will be obtained using the single breath occlusion technique⁹⁵. Functional residual capacity (FRC) will be obtained with the nitrogen washout technique with acceptance criteria as per ATS/ERS guidelines⁹⁴. Vital signs (respiratory rate, heart rate, oxygen saturation) will be continuously monitored during the testing. If a PFT does not meet the pre-specified technically acceptable criteria it can be reattempted in 24-48 hours.

d. Outpatient Infant Pulmonary Function Tests

Infant pulmonary function testing will be performed at 6 months of CGA (range of 5-8 months corrected age) at OHSU for all randomized patients. These will be primarily directed and performed by [name] who will be blinded to the NICU treatment allocation. [name] has experience with measurements of V_A, D_L,

and FEFs as these are the PFTs that were performed in the study at the Oregon National Primate Research Center examining the effect of CPAP on lung development. [name] RRT will also be a part of the research team performing the 6 month PFTs and he will be blinded as well. He was an integral part of the successful VCSIP study^{83,84} which measured FEFs at 3 and 12 months of age in offspring of pregnant smokers randomized to vitamin C versus placebo during pregnancy. Standard acceptance criteria will be applied. The PFT results will be reviewed off site for acceptability, reproducibility, and completeness by [name] and/or [name], RRT who has over ten years of experience in [name] PFT laboratory performing and interpreting these tests. They will be blinded to the treatment allocation in the NICU as will the statisticians at Indiana University performing the data analysis.

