All adverse events after randomization through discharge from the NICU and any adverse events after discharge deemed related or possibly related to the study (performance of the pulmonary function test done at 6 months of age with required sedation) will be recorded on the Adverse Events Log. Events will be reported to the IRB as per IRB policy and procedures. Adverse events (AEs) will be identified by review of the subject's electronic medical record (EMR), and by physical exam / observations (including vital signs monitoring during sedation). AEs will be graded as to their expectedness and attribution (unrelated, possibly, probably or definitely related to the protocol). The following standard definitions will be used:

i1. Definitions

Adverse Event (AE): Any untoward or undesirable, although not necessarily unexpected, event experienced by a human subject that may be a result of:

- The interventions and interactions use in the research
- The collection of identifiable private information in the research
- An underlying disease, disorder, or condition of the subject
- Other circumstances unrelated to the research or any underlying disease, disorder, or condition of the subject

Serious Adverse Event (SAE): Any AE that:

- Is fatal
- Is life-threatening
- · Is persistent or significantly disabling or incapacitating
- Results in inpatient hospitalization or prolongation of hospitalization
- Results in psychological or emotional harm requiring treatment
- Creates a persistent or significant disability
- Results in a significant medical incident (considered to be a serious study related event because, based upon appropriate medical judgment, it may jeopardize the subject and may require medical or surgical intervention to prevent one of the outcomes listed in this definition)

Unanticipated problems (UP): Events that are not expected given the nature of the research procedures and the subject population being studied and suggest that the research places subjects or others at a greater risk of harm or discomfort related to the research than was previously known or recognized. Harm to a subject need not occur for an event to be an unanticipated problem.

i2. Reporting of Adverse Events

All AEs, SAEs, and UPs should be documented on the appropriate adverse event logs/forms,(see Appendix B of DSMB charter) entered into the REDCap database, and reported to the study PI, [name], as outlined below.

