- All SAEs and UPs should be reported by to [name] within 1 business day.
- All other AEs should be entered into REDCap within 7 days.

[name] and her research team will evaluate each event and will determine reporting requirements. [name] and/or her research team will report events to the DSMB according to the following timeframes:

- All SAEs and UPs that require expedited reporting (SAEs that are deemed related, suspected to be
 related, and unexpected, all UPs) will be reported to the DSMB chair within 7 calendar days of the time
 the PI learns of the event.
- All other SAEs and AEs will be tabulated and reported to the DSMB at the next biannual meeting.

Additionally, the following events will also require expedited reporting:

- Neonatal or infant death through 1 year of age
- Any sedation related event requiring significant resuscitation and/or hospitalization

i3. Periodic Summary Reporting

All other AE's (that did not require expedited reporting as above) will be summarized biannually for the DSMB.

i4.Expected Risks

As detailed in the consent form, expected risks during the course of the study may include:

- Restlessness during PFTs in the NICU
- Pain during heel stick
- Embarrassing questions

- Skin breakdown around infant's nose or significant abdominal distension with feeding intolerance during the 2 weeks treatment period in infants randomized to eCPAP
- Increased respiratory distress with significant apnea during the 2 week treatment period in the infants randomized to dCPAP
- Sedation with chloral hydrate may include temporary disorientation, nervousness, excitement, dizziness, coughing, nausea, mild desaturations, obstruction of airway, apnea
- Breach of confidentiality

These risks are considered moderate and are addressed in the consent form.

The DSMB will meet twice per year by teleconference and review all other AEs/SAEs at that time. The DSMB will be composed of two neonatologists, a research ethicist (who may also serve as one of the neonatologists), a pediatric pulmonologist, and a statistician. Members of the NHLBI will also attend the DSMB meetings. See DSMB charter for further details. Minor protocol deviations will be documented in the subject's research chart. Major protocol violation will be reported to the IRB, per IRB guidelines.

7. Data Analysis

a. Sample Size Estimation and Power Considerations

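### The Adverse Events Log opens at randomization, but the first research procedure (the baseline NICU lung function test) comes before it, so capture of its adverse events is not assured

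*Protocol*

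**What the plan says.** **Order of events.** Protocol section 5.g (Consent Process) states: "Written informed consent will be obtained from each subject's parent/legal guardian prior to any study procedures taking place". Section 4.a (Overview) then says: "Prior to randomization and at the end of the 2 weeks of treatment, a pulmonary function test (PFT) will be performed". Section 6.c (Inpatient Infant Pulmonary Function Tests) agrees: "Infant pulmonary function testing will be performed when CPAP stability criteria is met prior to randomization". The Version 2.0 entry in the amendment history also mentions FRC measurement before randomization.

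**Recording window.** Section 6.i says that what is entered on the Adverse Events Log is "All adverse events after randomization through discharge from the NICU and any adverse events after discharge deemed related or possibly related to the study". This is the only sentence in either document that sets a time window for the log.

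**Other safety text in the protocol.**
- Section 6.i1 defines an adverse event broadly. The possible causes include "The interventions and interactions use in the research", and no start point is given.
- Section 6.i2 asks for every AE, SAE and unanticipated problem (UP) to be documented and entered in REDCap, again with no start point. SAEs and UPs go to the principal investigator within one business day. UPs, and any death through one year of age, go to the DSMB chair on an expedited basis.
- Section 6.i4 lists "Restlessness during PFTs in the NICU" among the expected risks.
- Section 6.c says: "Vital signs (respiratory rate, heart rate, oxygen saturation) will be continuously monitored during the testing".

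**SAP.** It says that the DSMB will review SAEs. It defines no safety population and no start of adverse event recording.

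**The concern.** From the baseline PFT onward, a consented infant is exposed to a research procedure for which the protocol itself lists a risk. The log window does not open until the next step, randomization. A coordinator who follows the window sentence would not log a non-serious event that occurs during or just after the baseline test.

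The case that matters most is an infant who becomes unstable around the test. Randomization requires the CPAP stability criteria to have been met for at least 12 hours (sections 5.c and 5.h). An infant who no longer met them might not be randomized, and would then never come inside the window. Such events would be the most informative about how well the test is tolerated, and the window sentence excludes them.

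What is at stake is the completeness of safety reporting for a study procedure, both in the tables that the DSMB sees and in the published account. The treatment comparison is not at stake.

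**Working it through.** The plan gives no figure to reproduce here. The check compares the order of events with the recording rules, followed by one subtraction.

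**Step 1: sequence.** Consent (5.g), then stability criteria met, then baseline PFT (4.a, 6.c), then randomization, then the log window opens (6.i). Appendix A places only consent and medical history before the first breathing test. The baseline PFT is therefore the first scheduled research test, and it lies outside the window.

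**Step 2: does other text close the gap?**

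| Provision | Tied to randomization? | Covers a non-serious event at the baseline PFT? |
|---|---|---|
| 6.i log window | Yes | No |
| 6.i2 general documentation rule | No | Yes on its face, but it conflicts with 6.i |
| 6.i2 SAE and UP reporting | No | Only if the event is serious or unanticipated |
| 6.i2 expedited death reporting | No | No |
| 8.a data forms for all consented infants | No | Unclear; adverse events are not mentioned |
| 5.i daily research-staff assessment | Yes | No |
| 6.c vital-sign monitoring | No | Observed, but no recording rule is attached |

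Two rows need comment.
- **6.i2 documentation rule.** If it had no time limit at all, it would also call for unrelated events after discharge, which 6.i excludes. It can therefore be read as setting forms and timelines within the 6.i window. It can equally be read literally, as covering everything. The text does not settle which governs.
- **UP route.** A UP must be unexpected for the procedures and the population. Restlessness is listed as expected (6.i4). The stability criteria themselves tolerate fewer than three self-resolving apneas, bradycardias or desaturations in an hour. The milder events that one would look for at this test may not qualify.

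**Step 3: size.** Inputs from section 5.a: "Up to 130 infants will be consented once inclusion/exclusion criteria have been verified", and 100 randomized.
- Randomized infants whose baseline PFT precedes the window: 100, if all are tested as planned. Technically unacceptable tests may be reattempted (6.c), so some infants may have more than one.
- Consented but not randomized: at most 130 − 100 = 30.
- Tested and then not randomized: between 0 and 30. Section 6.c ties the test to meeting the stability criteria, so a consented infant who never meets them is not tested. The documents do not allow a narrower range.

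No event rate for the NICU PFT is given, so the number of missed events cannot be estimated.

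**The case against.** The strongest reply is that section 6.i2, read literally, already requires these events to be documented. The definition in 6.i1 covers a consented infant who is undergoing a research test. SAEs, UPs and deaths are reported whether or not the infant has been randomized. The DSMB charter, which holds the adverse event forms, may cover the period and is not among the documents. The same test is repeated at the end of treatment, inside the window if done before discharge, so the DSMB would see something of its tolerability, though in older infants.

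Much of this stands, and it rules out three stronger conclusions that a reader might draw.
- **That harm from the baseline test is never recorded.** The documents do not support this. 6.i2 points the other way, serious and unanticipated events have their own routes, and an event that continues past randomization comes within the window.
- **That the risk is unmonitored.** Section 6.c requires continuous vital-sign monitoring during the test. The gap concerns logging and reporting.
- **That the test destabilizes infants or keeps them from being randomized.** The only NICU PFT risk listed is restlessness. Apnea and desaturation are listed for chloral hydrate sedation, which Appendix A confines to the six-month test; apnea is also listed for the CPAP-discontinuation arm. Loss of stability around the baseline test is a possibility that the log should be able to show, and the documents give no evidence that it happens.

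The reply does not remove the conflict. The one sentence that states a window excludes the baseline test, and staff cannot tell from the protocol whether that sentence or 6.i2 governs.

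**Conclusion.** The point holds as a conflict between section 6.i and section 6.i2. As worded, the log window excludes non-serious adverse events from the baseline NICU PFT, and their capture is not assured. This touches the baseline test in all 100 randomized infants and in 0 to 30 infants who are tested but not randomized.

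It would be possible to say that half of the scheduled NICU PFTs (100 of 200) fall outside the window. That share counts tests, not events, and assumes that every randomized infant has both tests, so it should not be taken as a measure of missed harm.

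The conclusion assumes that the protocol text governs. The DSMB charter could resolve the conflict, but that cannot be checked here. The events precede allocation, so the primary analysis and the between-arm adverse event comparison do not change. The correction is worth making because a stated rule leaves out a research procedure in a population that the protocol itself calls fragile, and it costs very little.

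**What to change.** - Reconcile 6.i with 6.i2. State that recording of AEs, SAEs and UPs starts at the first study procedure after consent (the baseline PFT) and applies to every consented infant who has it.
- State when recording ends for infants who are tested but not randomized. The sponsor should set this. The 24 to 48 hours in section 6.c is only the interval for repeating a technically unacceptable test and is not a safety basis for follow-up.
- Report pre-randomization procedural events to the DSMB on a separate line, not by arm, with the number of infants tested as the denominator.
- Keep the by-arm adverse event comparison starting at randomization.
- Check that the DSMB charter and its forms use the same start point.

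The cost is a short text change and one extra row in the safety report, with no added visits or tests.

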The incidence of prematurity is a health care crisis with significant economic and emotional costs in the United States (US) and worldwide. One of every 9-10 babies in the US²⁹, and an estimated 15 million babies worldwide^{29;30} are born preterm each year. Complications from preterm births are the leading cause of neonatal mortality and an important contributor to child and adult morbidities. In the US, the yearly estimated costs associated with preterm births are \$26.2 billion³¹⁻³³. All preterm infants have altered lung development with a high incidence of wheezy respiratory illnesses, hospitalizations, and asthma compared to full term infants³⁴. In preterm infants <37 weeks with and without BPD in the first year of life, the incidence of cough was reported to

be 79%, wheezing 44%, and respiratory re-hospitalizations $25\%^{35}$. A recent study in 537 infants born at < 28 wks gestation reported that 65% had post discharge respiratory disease and 71% had frequent wheeze or cough for \geq 6 months in the first year of life³⁶. *If eCPAP is demonstrated to stimulate lung growth and improve lung function, it could improve the respiratory health of up to 500,000 preterm infants yearly in the US and millions of preterm infants worldwide.*

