Forced Expiratory Flows (**FEF**₅₀) (**Secondary Outcome**) Measurements in triplicate will be obtained using the raised volume thoracic compression technique that we developed, and previously described^{74,75;83}.

Chloral hydrate sedation: Infant PFTs will be performed at Doernbecher Children's Hospital in sleeping infants following chloral hydrate sedation, as previously described^{68;74;84}. For testing, infants are examined by a physician and continuously monitored by a sedation nurse or health care provider certified in sedation and a respiratory therapist. The parents will be counseled about possible side effects, sign a separate sedation consent, and be given the patient education-discharge instructions. Safety will be monitored as outlined in the DSMB charter.

e. Respiratory Questionnaires

After discharge, a validated respiratory questionnaire will be administered monthly to the infant's primary caregiver ^{83;96} by research personnel blinded to the treatment allocation of eCPAP versus dCPAP in the NICU.. Caregivers are asked about new episodes of wheezing in the previous month, as well as administration of prescribed medications, other illnesses, trips to the emergency room, and hospitalizations. If an infant has wheezing associated with an illness lasting up to seven days, this will be counted as one episode. These questionnaires will be administered in person at the PFT done at approximately 6 months of CGA while the

remainder of the monthly questionnaires will be administered by phone. A small time reimbursement will be available for those patients after each questionnaire is completed.

f. Neurodevelopmental Testing

All preterm infants born at <34 GA are examined in the OHSU Developmental Evaluation Clinic (DEC) if born at OHSU or the PHSW DEC clinic if born at PHSW.at 6 -12 months CGA. This assessment is the standard practice of their care. We will document the Bayley IV neurodevelopmental scores for cognitive, receptive language, expressive language, fine motor, gross motor, and audiology results from these visits^{97;98}. The personnel performing this testing will be blinded to the treatment allocation of eCPAP versus dCPAP in the NICU.

g. Cohort Retention Methods

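### After NICU discharge the adverse event log is limited to PFT- and sedation-related events; this omits the allocated respiratory support and conflicts with the protocol's own all-SAE reporting rule

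*Protocol*

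**What the plan says.** **Scope of the log (Protocol 6.i).** Up to discharge it takes "All adverse events after randomization through discharge from the NICU". After discharge it takes only events "deemed related or possibly related to the study (performance of the pulmonary function test done at 6 months of age with required sedation", where the parenthesis closes. Two ways of finding events are named: review of the electronic medical record, and examination or observation.

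**Definitions (6.i1).** An adverse event may result from "Other circumstances unrelated to the research or any underlying disease, disorder, or condition of the subject", so relatedness is not part of the definition. One SAE criterion is "Results in inpatient hospitalization or prolongation of hospitalization".

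**Reporting (6.i2).** "All AEs, SAEs, and UPs should be documented on the appropriate adverse event logs/forms", and, for whatever is not expedited, "All other SAEs and AEs will be tabulated and reported to the DSMB at the next biannual meeting". Neither sentence stops at discharge or depends on attribution. Expedited reports cover related and unexpected SAEs, all unanticipated problems, deaths through 1 year, and sedation events needing significant resuscitation or hospitalization.

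**Other data (6.e).** Blinded staff question caregivers monthly after discharge, including on "trips to the emergency room, and hospitalizations".

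**SAP.** The appendix counts hospitalizations coded as bronchitis, bronchiolitis, wheezing or asthma, and breathing treatments given in hospital, as components of the wheeze outcome. The SAP has no safety analysis.

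**DSMB (8.d, 10.b3).** Its reports include adverse events together with safety and efficacy data, and its remit covers both.

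**The concern.** The treatment under test is two further weeks of CPAP against stopping it. The post-discharge rule ties relatedness to a different procedure, the 6-month PFT with its sedation. A new event after discharge that someone suspects is due to either arm does not fit that wording, nor does a readmission judged unrelated to the PFT.

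Benefit and harm are also followed over different periods. Lung function is measured at about 6 months, and Aim 3 asks whether allocation changes respiratory morbidity through 12 months. A plan that treats a late effect of allocation as plausible for benefit should be able to see one in the other direction.

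At stake is whether the DSMB and the final report would show post-discharge hospitalizations by arm. If they do not, a statement about harm would rest mainly on events before discharge.

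**Working it through.** The plan gives no figure to reproduce here. The check sets the rules side by side and then sizes the events they treat differently.

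**1. One test case under each rule.** Take an infant readmitted with bronchiolitis about four months after discharge, not linked to the PFT.

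| Rule | Result |
|---|---|
| 6.i, post-discharge scope | Not logged |
| 6.i1, SAE definition | An SAE (hospitalization) |
| 6.i2, documentation | Logged |
| 6.i2, twice-yearly tabulation | Goes to the DSMB |

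The sections give opposite instructions for the same event. The parenthesis in 6.i contains nothing that marks it as an example.

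**2. Do the other routes cover it?**
- Deaths and serious sedation events: not this case.
- Unanticipated problems: these must be unexpected and suggest greater risk than was known. A respiratory admission in a preterm-born infant will rarely qualify singly; only a comparison of arms would show an excess.
- Questionnaire: it captures the admission, but 6.i does not name it as an adverse event source.
- Wheeze composite: one positive answer on any questionnaire makes the infant positive. An admitted infant therefore scores the same as one whose parent once reported wheeze, and admissions for other reasons do not count as admissions.
- DSMB efficacy data: a possible route, but no section specifies hospitalizations by arm.

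**3. How long is full logging after treatment?** Using the pilot means in Protocol section 2.b3c (randomization 32.2 and 32.0 weeks; discharge 35.8 and 36.0 weeks) and 2 weeks of treatment:
- eCPAP: 35.8 − 32.2 − 2 = 1.6 weeks
- discontinuation: 36.0 − 32.0 − 2 = 2.0 weeks

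**4. How many infants?** The Introduction (2.a) cites "wheezing 44%, and respiratory re-hospitalizations" of 25% in the first year, for infants below 37 weeks with and without BPD. Expected count = infants followed × rate.

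| Infants followed | Basis | Expected at 25% |
|---|---|---|
| 100 | all randomized | 25 |
| 90 | after 10% NICU loss | 22.5 |
| 85 | 15% missing questionnaires | 21.25 |
| 76 | after both projected losses to the 6-month PFT | 19 |

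The documents give no rate for this trial's own population. Over an assumed range of 10% to 35%, the count runs from 76 × 0.10 = 7.6 to 100 × 0.35 = 35. Non-respiratory admissions would add to this, but no rate is given for them.

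**5. What could a by-arm table show?** Two-sided α = 0.05, normal approximation: power = Φ[(|p₁ − p₂| − 1.96·√(2p̄(1 − p̄)/n)) / √((p₁(1 − p₁) + p₂(1 − p₂))/n)].

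For 25% vs 40% with n = 50 per arm, p̄ = 0.325. The null standard error is √(0.43875/50) = 0.0937 and the alternative is √(0.4275/50) = 0.0925, so power = Φ[(0.15 − 0.1836)/0.0925] = Φ(−0.363) = 0.36.

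| n per arm | 25% vs 40% | 25% vs 50% |
|---|---|---|
| 50 | 0.36 | 0.74 |
| 45 | 0.33 | 0.69 |
| 42 | 0.31 | 0.66 |
| 38 | 0.28 | 0.62 |

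The 40% and 50% rates are assumptions. The table would be descriptive.

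**The case against.** The strongest reply is that this is a drafting conflict and does not prove that events are lost. Section 6.i2 is unrestricted, and if the site follows it, readmissions are logged and tabulated. Deaths and unanticipated problems are expedited whatever their link to the PFT. Hospitalizations are collected monthly under blinding, and the DSMB receives efficacy as well as safety data. Much of the safety detail is left to the DSMB charter, which is not among the documents. The harms that section 6.i4 expects of each arm (nasal breakdown, feeding intolerance, respiratory distress) are placed within the treatment period, and harm that starts in the NICU is logged at onset even if it persists.

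Most of this stands, and it rules out several stronger readings that a reader might infer:
- **That late harms and readmissions never reach the safety data or the DSMB.** The routes above contradict this. What is missing is an assured route.
- **That the DSMB would not see hospitalizations by arm.** The charter may provide for it, and nothing stops the DSMB asking.
- **That attribution after discharge is made by an unblinded team.** The NICU team is unblinded and the outcome assessors are blinded. The blinding of those who evaluate post-discharge events is not stated.
- **That a quarter of infants will have an unrecorded SAE.** The 25% comes from a wider population, applying it to all 100 ignores projected losses, and the admissions are recorded as questionnaire data.

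The reply does not remove the conflict between 6.i and 6.i2, or the omission of the allocated arms from the post-discharge wording. Nor does it point to any stated by-arm table.

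**Conclusion.** The point holds in a limited form and should be acted on. Section 6.i restricts post-discharge logging to PFT and sedation events, leaves out the randomized intervention, and contradicts 6.i2. Apart from deaths through 1 year, unanticipated problems and sedation events, new-onset late harms and readmissions have no assured place in the safety data.

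About 19 to 25 infants would have a respiratory readmission that the two sections treat differently (7.6 to 35 over the assumed 10% to 35%). This is indicative only. It assumes that the cited 25% carries over to stable infants born at up to 32 weeks, and that 76 to 100 of them are followed. Most such admissions would be background illness of prematurity. Nothing here suggests that either arm causes excess late harm; the issue is whether the plan would show it.

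**What to change.** 1. **Protocol 6.i and 6.i2:** reconcile them. Reword the post-discharge scope so that events possibly related to either allocated arm, the PFT or the sedation are logged through 12 months. State explicitly how SAEs judged unrelated are handled after discharge, so that one rule applies to a readmission.
2. **Protocol 6.i, sources:** name the monthly questionnaire as a source for SAEs.
3. **DSMB reports and SAP:** add a descriptive by-arm table of all-cause hospitalizations and emergency visits after discharge, with the number of infants and of events and the number of infants with questionnaire data as denominator. Use it in each twice-yearly DSMB report and in the final report. Check the DSMB charter first, in case it already provides this.

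The table is needed as well as the rewording, because most readmissions will not be judged related to either arm and would not enter the log through item 1 alone.

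The cost is protocol wording and one table from data already collected. The downside is more log entries, mostly background illness. With power of about 0.28 to 0.36 for an assumed 25% vs 40%, the table should be labelled as serving monitoring and transparent reporting, without a formal test. If follow-up is too far advanced for items 1 and 2, the final-report table can still be produced.
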